6.7 Other Safety Considerations

[figure not shown]
Any significant worsening noted during interim or final physical examinations, electrocardiogram, x-ray filming, any other potential safety assessment required or not required by protocol should also be recorded as a nonserious or serious AE, as appropriate, and reported accordingly.

[figure not shown]
7 DATA MONITORING COMMITTEE AND OTHER EXTERNAL COMMITTEES

Not applicable

8 STATISTICAL CONSIDERATIONS

8.1 Sample Size Determination

8.2 Populations for Analyses

- Enrolled subjects are those who signed an informed consent form and are assigned a Subject Identification number (PID)
- Randomized subjects are enrolled subjects who received a treatment assignment from the central randomization center
- Treated subjects are randomized subjects who received at least 1 dose of study therapy
- Follow-up subjects are treated subjects who continue into the follow-up period, as indicated on the end of treatment subject status Case Report Form (CRF).

8.3 Endpoints

Efficacy analyses will evaluate HCV RNA as measured by the Roche COBAS® AmpliPrep/COBAS® TaqMan® HCV Test (LLOQ = 15 IU/mL)

8.3.1 Primary Endpoint

Proportion of subjects with SVR₁₂, defined as HCV RNA < LLOQ, target detected (TD) or target not detected (TND) at follow-up Week 12 in all treated subjects. Missing HCV RNA data at follow-up Week 12 will be imputed using the Next Value Carried Backwards (NVCB) approach, i.e., missing HCV RNA data in the follow-up Week 12 window

will be imputed using the next and closest available HCV RNA measurement after the follow-up Week 12 HCV RNA window.

8.3.2 Key Secondary Endpoint

- The proportion of subjects who achieve SVR₁₂ in the presence and absence of baseline NS5A resistance-associated polymorphisms.

8.3.3 Secondary Endpoints

- On treatment safety, as measured by frequency of deaths, serious adverse events (SAEs), discontinuation due to adverse events (AEs), Grade 3/4 AEs and Grade 3/4 laboratory abnormalities;
- The proportion of subjects who achieve HCV RNA < LLOQ, TD or TND at each of the following Weeks: 1, 2, 4, 8, 12, 16, 20, 24, and EOT; post-treatment Week 4 and 24;
- The proportion of subjects who achieve HCV RNA <LLOQ, TND at each of the following Weeks: 1, 2, 4, 8, 12, 16, 20, 24, and EOT

8.3.4 Exploratory Endpoint(s)

8.4 Analyses

Results will be presented for treated subjects. Demographics, baseline characteristics and safety data will also be presented.

Categorical variables will be summarized using counts and percents. Continuous variables will be summarized with univariate statistics (eg, mean, median, standard deviation).

Longitudinal summaries of safety and efficacy endpoints will use pre-defined visit week windows. Windows around planned measurement times will be constructed based on the midpoint between planned study visits. Laboratory measures will be summarized using standard international values and units, and US units will be provided in the appendix.

On-treatment endpoints will be assessed using measurements from the start of study therapy through the last dose of study therapy plus 7 days. Follow-up endpoints will be assessed with measurements after the last dose of study therapy plus 7 days.

8.4.1 Demographics and Baseline Characteristics

The following will be summarized by treatment for treated subjects:

- Demographics including: gender, age, race and ethnicity
- Physical measurements at baseline: height, weight, body mass index (BMI)
- Disease characteristics at baseline: HCV RNA level, IL28B SNP genotype, HIV positive, and fibrosis stage
- Laboratory tests at baseline
- Prior medications. Prior medications are those taken before the first dose of study therapy

8.4.2 Efficacy Analyses

Efficacy endpoints during the on-treatment period will be based on HCV RNA measurements closest to the planned visits within pre-defined visit windows. Efficacy endpoints during the follow-up period will be based on the last HCV RNA measurements in pre-defined visit windows.

The primary analysis for the proportions of patients meeting the efficacy endpoints will be for all treated subjects.

For binary efficacy endpoints including secondary efficacy endpoints, response rates and 2-sided 95% exact Binomial confidence intervals (CIs) will be estimated for each treatment arm.

8.4.2.1 Primary Efficacy

The primary analysis will be performed after all subjects have completed post-treatment Week 12 (SVR12). A final analysis (SVR24) will be performed at study completion.

The primary analysis for the primary endpoint SVR12 will use all treated subjects, and missing HCV RNA data at follow-up Week 12 will be imputed using the Next Value Carried Backwards (NVCB) approach, ie, missing HCV RNA data in the follow-up Week 12 window will be imputed using the next and closest available HCV RNA measurement after the follow-up Week 12 HCV RNA visit window.

The lower bound of the SVR12 95% confidence interval (CI) will be used to compare to the historical threshold of 79%. If it exceeds 79%, it can be concluded that the primary objective is achieved.

The following sensitivity analyses on the primary endpoint will also be conducted:

- Sensitivity analysis using mITT: SVR12 rates and two-sided 95% CIs will use all treated subjects. The SVR12 status for subjects with missing follow-up Week 12 HCV RNA will be counted as non-responders
- Sensitivity analysis using observed values: SVR12 rates and two-sided 95% CIs will use observed values. The numerator is based on subject meeting the response criteria. However, the denominator is based on treated subjects with HCV RNA at post-treatment Week 12

8.4.2.2 Secondary Efficacy

The following efficacy endpoints will be summarized for treated subjects:

- The proportion of subjects who achieve HCV RNA < LLOQ, TD/TND at each of the following Weeks: 1, 2, 4, 8, 12, 16, 20, 24 and EOT; post-treatment Week 4 and 24
- The proportion of subjects who achieve HCV RNA < LLOQ, TND at each of the following Weeks: 1, 2, 4, 8, 12, 16, 20, 24 and EOT

8.4.3 Safety Analyses

Safety data will be summarized for treated subjects.

Deaths will be listed for enrolled subjects regardless of onset.

The frequencies of the following safety events will be summarized by study period (on treatment and follow-up) for treated subjects:

- SAEs
- AEs leading to discontinuation of study therapy (regardless of onset)
- AEs by intensity
- Laboratory abnormalities by toxicity grade

The investigators should determine the grade of AEs according to the Division of AIDS (DAIDS) of the US National Institutes of Health Table for Grading the Severity of Adult and Pediatric Adverse Events (2004) ([Appendix 2](#)). The investigators' terms will be coded and grouped by system organ class using the latest version of the Medical Dictionary for Regulatory Activities (MedDRA) in production at BMS. AEs will be presented by system organ class and preferred term. Presentations will include both non-serious and SAEs, unless otherwise specified. If a subject had an AE with different intensities over time, only the worst grade will be reported for a study period.

Laboratory toxicities will be graded according to the Division of AIDS (DAIDS) of the US National Institutes of Health Table for Grading the Severity of Adult and Pediatric Adverse Events (2004) ([Appendix 2](#)). The laboratory value during the study period with the worst grade will be reported for each test.

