- h) Known history of genetic coagulopathy including, but not limited to, hemophilia;
- i) Uncontrolled diabetes (any subject with a confirmed screening HbA1c ≥ 8.5 must be excluded);
- j) Confirmed, uncontrolled hypertension (any screening systolic blood pressure ≥ 160 mmHg or diastolic blood pressure ≥ 100 mmHg should be excluded);
- k) Active substance abuse as defined by DSM-IV, Diagnostic Criteria for Drug and Alcohol Abuse ([Appendix 1](#)), which in the opinion of the investigator would make the candidate inappropriate for participation in this study
- l) Active severe psychiatric disorders including but not limited to, schizophrenia, psychosis, bipolar disorder, post-traumatic stress disorder, mania, etc.;
- m) Inability to tolerate oral medication;
- n) Poor venous access that would impair the subject's ability to comply with the study protocol;
- o) Prior NS5A treatment failures;

- p) Discontinuations of prior SOF/RBV treatment due to intolerance and/or exacerbations of anemia;
- q) Subjects infected with HIV-2;
- r) Presence of AIDS-defining opportunistic infections or any AIDS diagnosis within 12 weeks prior to study entry (AIDS-defining opportunistic infections as defined by the CDC);
- s) The following conditions are exclusion criteria for the use of RBV, based on the label:
 - i. History of hemoglobinopathies (eg, thalassemia major or sickle cell anemia), diagnoses associated with an increased baseline risk for anemia (eg, spherocytosis), hemolytic anemia, or diseases in which anemia would be medically problematic;
 - ii. History of cardiomyopathy, active unstable coronary artery disease (including angina), ventricular arrhythmia, congestive heart failure (other than fluid overload due to hepatic insufficiency), pulmonary hypertension or other clinically significant cardiac disease;
 - iii. Historical or current electrocardiogram (ECG) finding indicative of cardiovascular instability, including but not limited to evidence of myocardial ischemia, unstable re-entry phenomena, other significant dysrhythmias, and/or uncontrolled hypertension
 - iv. History of hypersensitivity to drugs with a similar biochemical structure to RBV;
 - v. Any other criteria that would exclude the subject from receiving RBV, per the local label

3) Physical and Laboratory Test Findings

- a) Alanine aminotransferase (ALT) $\geq 10x$ ULN

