- b) Total bilirubin ≥ 2 mg/dL (≥ 34 μ mol/L), unless due to Atazanavir/Ritonavir treatment or subject has a documented history of Gilbert's disease
- c) Albumin < 3.0 g/dL (30 g/L);
- d) Platelets $< 50 \times 10^3$ cells/ μ L;
- e) ANC $< 0.75 \times 10^3$ cells/ μ L;
- f) Hemoglobin < 10 g/dL (100 g/L);
- g) Creatinine Clearance (CrCl) ≤ 50 mL/min (as estimated by Cockcroft and Gault);
- h) Alpha fetoprotein (AFP):
 - i. AFP > 100 ng/mL (> 82.6 IU/mL) **OR**
 - ii. AFP ≥ 50 and ≤ 100 ng/mL (≥ 41.3 IU/mL and ≤ 82.6 IU/ mL) requires a liver ultrasound and subjects with findings suspicious for HCC are excluded.
- i) QTcF or QTcB > 500 mSec

4) Allergies and Adverse Drug Reaction

- a) History of hypersensitivity to drugs with a similar biochemical structure to DCV, SOF, and RBV
- b) Any other criteria or known contraindication that would exclude the subject from receiving DCV, SOF, and RBV

5) Prohibited Treatments and/or Therapies

- a) Exposure to any investigational drug or placebo within 4 weeks of study drug administration
- b) Use of amiodarone for 60 day time period prior to start of treatment

Refer to [Section 3.4.1](#) for prohibited and/or restricted treatments during treatment, re-treatment and post-treatment

6) Sex and Reproductive Status

- a) Males and females who do not or cannot meet the requirements outlined in Inclusion Criteria 3
- b) Male subjects must confirm that their female sexual partners are not pregnant at the time of screening

7) Other Exclusion Criteria

- a) Prisoners or subjects who are involuntarily incarcerated. (Note: under certain specific circumstances a person who has been imprisoned may be included or permitted to continue as a subject. Strict conditions apply and Bristol-Myers Squibb approval is required).
- b) Subjects who are compulsorily detained for treatment of either a psychiatric or physical (eg, infectious disease) illness
- c) Any other medical, psychiatric, and/or social reason which, in the opinion of the investigator would make the subject inappropriate for the study

Eligibility criteria for this study have been carefully considered to ensure the safety of the study subjects and that the results of the study can be used. It is imperative that subjects fully meet all eligibility criteria.

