4.3 Secondary Endpoints

- On treatment safety, as measured by frequency of deaths, SAEs, discontinuations due to AEs, Grade 3/4 AEs, and Grade 3/4 laboratory abnormalities through the end of treatment plus 7 days;
- The proportion of subjects who achieve HCV RNA < LLOQ, TD or TND at each of the following Weeks: 1, 2, 4, 8, 12, 16, 20, 24, and EOT; post-treatment Weeks 4 and 24;
- The proportion of subjects who achieve HCV RNA < LLOQ, TND at each of the following Weeks: 1, 2, 4, 8, 12, 16, 20, 24, and EOT.

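### As written, the Grade 3/4 laboratory count does not separate ALT, AST and exempt-bilirubin abnormalities present before dosing from those that arise on treatment

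*Protocol*

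**What the plan says.** Protocol 8.4.3 summarizes laboratory abnormalities by toxicity grade and study period, using the DAIDS table in Appendix 2. Where a test is repeated, the rule is: "The laboratory value during the study period with the worst grade will be reported for each test".

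The period is defined by dates alone. Protocol 8.4 states: "On-treatment endpoints will be assessed using measurements from the start of study therapy through the last dose of study therapy plus 7 days". SAP 4.3 lists the secondary safety endpoint with the same limit: "Grade 3/4 laboratory abnormalities through the end of treatment plus 7 days". None of these places mentions the pre-dose grade. Protocol 8.4.1 plans a summary of baseline laboratory results but does not link it to the on-treatment grades.

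Protocol 3.3.2 (Exclusion Criteria, item 3) excludes ALT only at 10 x ULN or above. It caps total bilirubin below 2 mg/dL "unless due to Atazanavir/Ritonavir treatment or subject has a documented history of Gilbert's disease". It gives no AST limit.

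SAP 7.6 refers safety analyses to Core SAP 7.6 (7.6.1 to 7.6.11), and SAP 6.1 refers study periods to Core SAP 6.1. Neither text is available. The footnote to SAP Table 8.1-1 leaves the classification of Day 1 measurements, as pre-treatment or on-treatment, to that section.

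**The concern.** Subjects enter with active hepatitis C and cirrhosis, so raised transaminases before dosing are to be expected. A rule that takes the worst on-treatment grade without reference to baseline counts a high value that was already there in the same way as one that appears after dosing.

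Safety is half of the research hypothesis (Protocol 1.2), and there is one arm. In a controlled trial the comparator rate would show how much Grade 3 ALT belongs to the disease. Here the observed rate will be read directly as the toxicity of the regimen. The same endpoint list also counts Grade 3/4 adverse events, which Protocol 6 defines as new or worsening. One safety endpoint therefore combines a baseline-referenced count with one that, as written, is not.

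**Working it through.** The plan states no rate, power or precision for the laboratory endpoint, so it has no figure to reproduce. The check has three steps.

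**1. What can be present at entry.** Take the most abnormal value each entry limit in Protocol 3.3.2 admits and read its grade from Appendix 2.

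| Test | Most abnormal value admitted | DAIDS grade | Grade 3/4 at entry? |
|---|---|---|---|
| ALT | just under 10 x ULN (Grade 3 is 5.1 to 10.0 x ULN) | 3 | Yes |
| AST | no limit stated | up to 4 | Yes |
| Bilirubin, exempt groups | no limit (Grade 3 starts at 2.6 x ULN) | up to 4 | Yes |
| Bilirubin, others | 1.99 mg/dL | 2 | No |
| Platelets | 50,000 | 2 | No |
| ANC | 750 | 2 | No |
| Hemoglobin (absolute) | 10.0 g/dL | 1 | No |
| Albumin | 3.0 g/dL | 1 | No |

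The row for other bilirubin subjects assumes a ULN of 1.0 to 1.3 mg/dL: 1.99/1.0 = 1.99 and 1.99/1.3 = 1.53 x ULN. Both are Grade 2, because Appendix 2 assigns a value between two grades to the higher one.

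**2. How it enters the count.** Screening values lie outside the on-treatment period. A pre-existing abnormality is counted if it persists into an on-treatment sample. Whether Day 1 samples qualify is left open, but the Week 1 window in SAP Table 8.1-1 (days 5 to 11) is on-treatment. As an example, a subject at 9 x ULN before dosing and 6 x ULN at Week 1 has improved by (9 - 6)/9 = 33%. The subject is still Grade 3 and is counted.

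**3. Possible size, under assumption.** Let q be the share of subjects with a Grade 3/4 value before dosing and r the share of those still at Grade 3/4 on treatment. The documents give neither. Expected carried-over subjects = 75 x q x r.

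| q | r = 25% | r = 100% |
|---|---|---|
| 2% | 0.4 (0.5 points) | 1.5 (2 points) |
| 5% | 0.9 (1.25 points) | 3.75 (5 points) |
| 10% | 1.9 (2.5 points) | 7.5 (10 points) |

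For scale, the exact (Clopper-Pearson) 95% interval is 0% to 4.8% for 0/75 and 1.5% to 13.1% for 4/75. A few carried-over subjects would therefore change how the result reads. The same routine gives 81.7% to 96.2% for 68/75, matching SAP Table 5.1-1.

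**The case against.** The strongest objection is that the governing text is not available. A reader might infer that the plan makes no baseline comparison anywhere. The documents do not support that: SAP 7.6 sends all safety methods to the Core SAP, which may define treatment-emergent abnormalities. The protocol sentence only picks one value among repeats and is compatible with such a rule. This stands, and it limits the point to what Protocol 8.4.3 and SAP 4.3 themselves say.

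Other stronger readings also fail:

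- **That Day 1 samples are counted as on-treatment.** The footnote to SAP Table 8.1-1 leaves this open. The mechanism needs only persistence to Week 1.
- **That all laboratory tests are affected.** Four of the capped tests cannot enter at Grade 3/4, and hemoglobin in HIV-negative subjects is already graded partly on the fall from baseline.
- **That glucose is a further route.** Protocol 3.3.2 allows HbA1c below 8.5 and fasting is not required, but nothing in the documents links this to Grade 3 glucose (251 mg/dL or more).
- **That the rule makes the regimen look safer.** It over-counts toxicity, and a move from Grade 3 to Grade 4 stays visible because results are given by grade.

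It is also fair that the endpoint is descriptive, with no threshold attached, and that other rules already use baseline: the adverse event definition (Protocol 6), potential liver injury (6.6) and the ALT discontinuation criterion (3.5). These do not change how the Grade 3/4 laboratory table is built.

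Finally, replacing the worst-grade count with a strict worse-than-baseline count would lose a subject who enters at Grade 3, improves, and returns to Grade 3 on treatment. That is a good reason to add to the current summary and not to replace it.

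**Conclusion.** The point holds for the rule as written in Protocol 8.4.3 and SAP 4.3. Grade 3/4 ALT, AST and exempt bilirubin values that pre-date treatment, and are still present at Week 1 or later, are counted with those that arise on treatment. With no control arm the two cannot be told apart from the planned table. The direction is over-counting of toxicity.

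The size cannot be derived from the documents. The range of 0.4 to 7.5 subjects (0.5 to 10 percentage points) rests wholly on assuming that 2% to 10% enter at Grade 3/4 and that 25% to 100% of these persist. The conclusion for the unaffected tests rests on the entry limits, and for non-exempt bilirubin also on the assumed ULN. The primary SVR12 analysis is not touched. If the Core SAP already defines emergence, what remains is a missing citation and an unaligned protocol sentence.

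**What to change.** Keep the worst-grade summary. In Protocol 8.4.3 and SAP 7.6, add:

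- (a) a count of subjects with an on-treatment Grade 3/4 value higher than the last pre-dose grade for that test, also counting a return to Grade 3/4 after an on-treatment improvement to a lower grade;
- (b) a table of baseline grade by worst on-treatment grade for ALT, AST and total bilirubin.

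State which sample supplies the pre-dose grade, including how Day 1 values are classed. If Core SAP 7.6 already defines emergence, cite the subsection and align the protocol sentence with it.

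The cost is some wording, one extra count and one extra table, all from data already collected. The rebound clause in (a) is needed because the shift table alone would show Grade 3 to Grade 3 for both persistence and rebound.

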8.4.4 Pharmacokinetic Analyses

8.4.6 *Outcomes Research Analyses*

Not Applicable

8.4.7 *Pharmacodynamics*

8.4.8 *Other Analyses*

Analyses for the frequency of genotypic substitutions at baseline, and post-baseline associated with virologic failure for each treatment will be conducted.

8.5 *Interim Analyses*

The primary analysis will be performed after all subjects have completed post-treatment Week 12 (SVR12). A final analysis (SVR24) will be performed at study completion. Additional interim efficacy analyses may be performed prior to post-treatment Week 12 to support external data presentations or for correspondences with health authorities.

9 *STUDY MANAGEMENT*

9.1 *Compliance*

9.1.1 *Compliance with the Protocol and Protocol Revisions*

The study shall be conducted as described in this approved protocol. All revisions to the protocol must be discussed with, and be prepared by, BMS. The investigator should not implement any deviation or change to the protocol without prior review and documented approval/favorable opinion from the IRB/IEC of an amendment, except where necessary to eliminate an immediate hazard(s) to study subjects.

If a deviation or change to a protocol is implemented to eliminate an immediate hazard(s) prior to obtaining IRB/IEC approval/favorable opinion, as soon as possible the deviation or change will be submitted to:

- IRB/IEC for review and approval/favorable opinion
- BMS

- Regulatory Authority(ies), if required by local regulations

Documentation of approval signed by the chairperson or designee of the IRB(s)/IEC(s) must be sent to BMS.

If an amendment substantially alters the study design or increases the potential risk to the subject: (1) the consent form must be revised and submitted to the IRB(s)/IEC(s) for review and approval/favorable opinion; (2) the revised form must be used to obtain consent from subjects currently enrolled in the study if they are affected by the amendment; and (3) the new form must be used to obtain consent from new subjects prior to enrollment.

If the revision is done via an administrative letter, investigators must inform their IRB(s)/IEC(s).

9.1.2 *Monitoring*

BMS representatives will review data centrally to identify potential issues to determine a schedule of on-site visits for targeted review of study records.

Representatives of BMS must be allowed to visit all study site locations periodically to assess the data quality and study integrity. On site they will review study records and directly compare them with source documents, discuss the conduct of the study with the investigator, and verify that the facilities remain acceptable.

In addition, the study may be evaluated by BMS internal auditors and government inspectors who must be allowed access to CRFs, source documents, other study files, and study facilities. BMS audit reports will be kept confidential.

The investigator must notify BMS promptly of any inspections scheduled by regulatory authorities, and promptly forward copies of inspection reports to BMS.

9.1.2.1 *Source Documentation*

The Investigator is responsible for ensuring that the source data are accurate, legible, contemporaneous, original and attributable, whether the data are hand-written on paper or entered electronically. If source data are created (first entered), modified, maintained, archived, retrieved, or transmitted electronically via computerized systems (and/or any other kind of electronic devices) as part of regulated clinical trial activities, such systems must be compliant with all applicable laws and regulations governing use of electronic records and/or electronic signatures. Such systems may include, but are not limited to, electronic medical/health records (EMRs/EHRs), adverse event tracking/reporting, protocol required assessments, and/or drug accountability records).

When paper records from such systems are used in place of electronic format to perform regulated activities, such paper records should be certified copies. A certified copy consists of a copy of original information that has been verified, as indicated by a dated signature, as an exact copy having all of the same attributes and information as the original.

9.1.3 *Investigational Site Training*

Bristol-Myers Squibb will provide quality investigational staff training prior to study initiation. Training topics will include but are not limited to: GCP, AE reporting, study details and procedure, electronic CRFs, study documentation, informed consent, and enrollment of WOCBP.

9.2 *Records*

9.2.1 *Records Retention*

The investigator must retain all study records and source documents for the maximum period required by applicable regulations and guidelines, or institution procedures, or for the period specified by BMS, whichever is longer. The investigator must contact BMS prior to destroying any records associated with the study.

BMS will notify the investigator when the study records are no longer needed.

If the investigator withdraws from the study (eg, relocation, retirement), the records shall be transferred to a mutually agreed upon designee (eg, another investigator, IRB). Notice of such transfer will be given in writing to BMS.

9.2.2 *Study Drug Records*

It is the responsibility of the investigator to ensure that a current disposition record of study drug (inventoried and dispensed) is maintained at the study site to include investigational products. Records or logs must comply with applicable regulations and guidelines and should include:

- amount received and placed in storage area
- amount currently in storage area
- label identification number or batch number
- amount dispensed to and returned by each subject, including unique subject identifiers
- amount transferred to another area/site for dispensing or storage
- nonstudy disposition (eg, lost, wasted)
- amount destroyed at study site, if applicable
- amount returned to BMS
- retain samples for bioavailability/bioequivalence, if applicable
- dates and initials of person responsible for Investigational Product dispensing/accountability, as per the Delegation of Authority Form.

BMS will provide forms to facilitate inventory control if the investigational site does not have an established system that meets these requirements.

9.2.3 *Case Report Forms*

An investigator is required to prepare and maintain adequate and accurate case histories designed to record all observations and other data pertinent to the investigation on each individual treated or entered as a control in the investigation. Data that are derived from source documents and

reported on the CRF must be consistent with the source documents or the discrepancies must be explained. Additional clinical information may be collected and analyzed in an effort to enhance understanding of product safety. CRFs may be requested for AEs and/or laboratory abnormalities that are reported or identified during the course of the study.

For sites using the BMS electronic data capture tool, electronic CRFs will be prepared for all data collection fields except for fields specific to SAEs and pregnancy, which will be reported on the electronic SAE form and Pregnancy Surveillance form, respectively. If electronic SAE form is not available, a paper SAE form can be used. Spaces may be left blank only in those circumstances permitted by study-specific CRF completion guidelines provided by BMS.

The confidentiality of records that could identify subjects must be protected, respecting the privacy and confidentiality rules in accordance with the applicable regulatory requirement(s).

The investigator will maintain a signature sheet to document signatures and initials of all persons authorized to make entries and/or corrections on CRFs.

The completed CRF, SAE/pregnancy CRFs, must be promptly reviewed, signed, and dated by the investigator or qualified physician who is a subinvestigator and who is delegated this task on the Delegation of Authority Form. For electronic CRFs, review and approval/signature is completed electronically through the BMS electronic data capture tool. The investigator must retain a copy of the CRFs including records of the changes and corrections.

Each individual electronically signing electronic CRFs must meet BMS training requirements and must only access the BMS electronic data capture tool using the unique user account provided by BMS. User accounts are not to be shared or reassigned to other individuals.

